### 5.3.1.4. Analysis of Secondary Immunogenicity Objectives

The statistical hypotheses associated with the non-inferiority tests in the secondary immunogenicity objectives are described as below:

$$H_0 : \mu_A - \mu_B \leq \delta \text{ vs. } H_{1j} : \mu_A - \mu_B > \delta$$

Where  $\delta$  denotes the non-inferiority margin, and  $\mu_A$  and  $\mu_B$  denote either the means of log 10-transformed concentrations/titers or the percentage of subjects achieving the threshold response for binary variables.

Note that statistical hypotheses testing is not applicable for the seroresponse rates of antigens tested for Polio, MMR and VV vaccines. Instead, descriptive analysis will be performed. For each antigen tested, the percentage of subjects with anti-polio type 1, 2 and 3 neutralization antibody titers  $\geq 8$ , or the percentage of subjects with post-vaccination anti-measles, anti-rubella, anti-mumps and anti-VZV virus antibody concentration  $\geq$  a protective threshold (see protocol table 22) will be presented as point estimates along with the associated 2-sided 95% Clopper-Pearson CIs.

#### *Statistical Methods*

Concentration and titer data will be summarized by vaccine group, strain and time point. Additionally, within-subject GMRs will be computed for GMTs at one month after 4th vaccination versus pre-4th vaccination. As for GMTs/GMCs, the GMRs/GMCs and 95% CIs will be computed by exponentiating (base 10) the corresponding means and 95% CIs from an ANOVA model.

For the binary variables, for example, percentage of subjects with hSBA titer  $\geq$  LLOQ, percentage of subjects with serum pneumococcal anti-capsular polysaccharide IgG  $\geq 0.35$   $\mu\text{g/ml}$ , the number and percentage of subjects and associated 2-sided 95% Clopper-Pearson CIs (available in SAS Procedure PROC FREQ, [Frank, 2009 ;Clopper, 1934]) will be computed for each antigen/strain by vaccine group and by time-point.

Between group-differences with 95% CIs will also be derived using the Miettinen and Nurminen method [Miettinen, 1985].

### 5.3.2. Additional considerations

The log10-transformed antibody titers/concentrations at one month after the 3rd, pre-4th, and one month after the 4th vaccination will be analysed using an additive two-way Analysis of Variance (ANOVA) model which includes the vaccine-group effect, and a center effect. Summary tables will show adjusted geometric mean titers (GMTs) and/or geometric mean concentrations (GMCs) and adjusted ratios of GMTs / GMCs for each vaccine group.

Binary data tables will show unadjusted percentages and adjusted “between-group” differences (adjusted for center). The Miettinen and Nurminen method [Miettinen, 1985] will be applied.

Descriptive summary statistics will be provided for subgroups gender, race, ethnic origin and age group (6-8 weeks or  $\geq 8$  weeks), for the following parameters:

- GMCs for PCV at one month after the 3rd and 4th vaccination.
- Percentages of subjects with hSBA titer  $\geq$  LLOQ; for each of the 4 rMenB+OMV NZ test strains and for all strains combined, at each timepoint that a blood sample result will be available, in Group MenB+PCV and Group Placebo+PCV.
- Percentages of subjects with hSBA titers  $\geq 8$  (for strains M14459, NZ98/254, M13520) and  $\geq 16$  (for strain 96217); for each of the 4 rMenB+OMV NZ test strains and for all strains combined at one month after the 4th vaccination in Group MenB+PCV and Group Placebo+PCV.

Subgroup analyses will be performed on the FAS.

The MenB serum bactericidal assay (hSBA) limits to be applied to the analyses will be as follows:

Assay	LOD	LLOQ
M14459 (fHbp)	4	5
96217 (NadA)	6	14
NZ98/254 (PorA)	4	6
M13520 (NHBA)	4	6

Seroresponse for varicella will be defined as post-vaccination anti-VZV gE IgG concentration  $\geq 300$  mIU/mL among subjects who were seronegative (antibody concentration  $<$  assay cut-off) before vaccination. The assay cut-off will be the LLOQ = 97.0 mIU/mL (anti-gE ELISA).

Seroresponse of MMR will be defined as post-vaccination anti-measles virus, anti-mumps virus and anti-rubella virus antibody concentration  $\geq$  a protective threshold among subjects who were seronegative (antibody concentration  $<$  assay cut-off) before vaccination (MMR Luminex assay).

Thresholds and cut-off values are presented below:

	Measles (mIU/mL)	Mumps (AU/mL)	Rubella (IU/mL)
Threshold	116	296	24
Cut-off = LLOQ	29.082	189.240	1.916

### 5.3.2.1. Sensitivity analyses due to the administration of PCV20 at Visit 5

The following analyses will be performed excluding subjects who did receive PCV20 at Visit 5:

- Numbers and percentages of subjects with hSBA titers  $\geq 8$  (for strains M14459, NZ98/254, M13520) and  $\geq 16$  (for strain 96217) for each of the 4 rMenB+OMV NZ

test strains and for all strains combined (composite endpoint) at one month after the 4th vaccination in Group MenB+PCV and Group Placebo+PCV with their associated 2-sided 95% Clopper-Pearson CIs.

- ECL GMCs for each of the 13 PCV13 antigens with their 2-sided 95% CIs at one month after the 4th vaccination in Group MenB+PCV and Group Placebo+PCV.
- Numbers and percentages of subjects with serum pneumococcal anti-capsular polysaccharide IgG  $\geq 0.35$   $\mu$ g/mL for each of the 13 PCV13 antigens at one month after the 4th vaccination in Group MenB+PCV and Group Placebo+PCV with their associated 2-sided 95% Clopper-Pearson CIs.
- Between-group GMC ratios (i.e. study group minus control group) against measles, mumps, rubella and VZV antigens at one month after the 4th vaccination with their associated 2-sided 95% CIs.
- Numbers and percentages of subjects with hSBA titers  $\geq$ LLOQ for each of the M14459, 96217, NZ98/254 and M13520 test strains at one month after the 4th vaccination in Group MenB+PCV and Group Placebo+PCV with their associated 2-sided 95% Clopper-Pearson CIs.
- Numbers and percentages of subjects with hSBA titers  $\geq 5$  for each of the M14459, 96217, NZ98/254 and M13520 test strains at one month after the 4th vaccination in Group MenB+PCV and Group Placebo+PCV with their associated 2-sided 95% Clopper-Pearson CIs.
- hSBA GMTs and within group geometric mean ratios (GMRs) for post 4th vaccination over pre-4th vaccination against each of the M14459, 96217, NZ98/254 and M13520 test strains.
- Numbers and percentages of subjects with 4-fold increase in hSBA titers (at post 4th vaccination from pre-4th vaccination) for each of the M14459, 96217, NZ98/254 and M13520 test strains.

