
 To demonstrate the immunological non-inferiority of MMR and VV vaccines when administered concomitantly with rMenB+OMV NZ and PCV13 to healthy subjects at 12 months compared to MMR and VV vaccines concomitantly administered with PCV13, without rMenB+OMV NZ, at one month after vaccination. 
Criterion: The immunological non-inferiority will be demonstrated if the lower limit of the 2-sided 95% CI for the between-group ratio of GMCs is >0.67 at one month after the MMR and VV vaccinations.
	
 At 1 month after the 4th vaccination (Day 331): 
 GMCs against measles, mumps, rubella and VZV antigens.

 To evaluate the immune response to rMenB+OMV NZ when administered concomitantly with PCV13 and other RIV to healthy infants at 2, 4, 6 and 12 months of age, at one month after the 3rd vaccination, at 6 months after the 3rd vaccination (immediately before the 4th vaccination), and at one month after the 4th vaccination against the M14459, 96217, NZ98/254 and M13520 test strains. 	
 At 1 month after the 3rd vaccination (Day 151) 
 the percentages of subjects with hSBA titers ≥ 5, ≥ 8 and ≥ 16 for each of the M14459, 96217, NZ98/254 and M13520 test strains. the hSBA geometric mean titers (GMTs) against each strain. At 6 months after the 3rd vaccination (Day 301, immediately before the 4th vaccination):

CONFIDENTIAL

205239 (MENB REC 2ND GEN-023 [V72_57])

Protocol Amendment 8 Final

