5.2.3. Allocation of subjects to assay subsets

For the analysis of the immune responses to the RIV antigens, subjects in each of the 2 study groups will be randomly assigned to different immunogenicity subsets. The assignment of the immunogenicity subsets will be performed by a second randomization, whereas the first randomization will be performed at the enrolment to assign subjects to Group MenB+PCV or Group Placebo+PCV.

Group MenB+PCV: All 800 subjects will be randomly assigned into one of the 3 immunogenicity subsets:

- Subset A1: 400 subjects
- Subset A2: 200 subjects
- Subset A3: 200 subjects

Group Placebo+PCV: A total of 400 subjects will be randomly assigned into 2 immunogenicity subsets:

- Subset B1: 200 subjects
- Subset B2: 200 subjects

The different subsets against which the different antigens will be tested are described in [Table 9](#). Testing of diphtheria, tetanus, pertussis, polio, HepB and Hib antigens will be performed at Visit 4 (post-3rd vaccination). Testing of MMR and VV will be done at Visit 5 (pre-4th vaccination) and Visit 6 (post-4th vaccination). In addition, subjects from subset B1 (200 subjects) will also be tested against the 4 serogroup B strains at all 3 timepoints in order to maintain the observer-blindness of the study during the blood sample testing.

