Determination of the Immunogenicity Subsets Sizes for the Secondary Objectives:

As described in detail in [Table 9](#), due to limited serum volume available subjects will be randomly assigned to test different sets of RIV antigens. Subjects will either be assigned to subset A1, A2, A3 in Group MenB+PCV or assigned to subset B1 and B2 in Group Placebo+PCV (see Section [5.2.3](#)). The below tables ([Table 21](#) and [Table 22](#)) show the likelihood to achieve non-inferiority for each of the RIV antigens (excluding polio) with the proposed sample sizes for immunogenicity subsets.

Table 21 Non-inferiority to Each Individual Antigen (excluding polio antigens) in Pediarix and Hiberix, at One Month After 3rd Dose of rMenB+OMV NZ

Component	Endpoint	Non-inferiority Margin	Reference		# Evaluable Subjects per Immunogenicity Subset (MenB group/Placebo group)*	Power
			Difference in %/ratio (Co-ad vs routine)	% in Routine group or SD		
Diphtheria	%≥0.1IU/mL	10%	Diff=0%	99.4%	240/120	>99.9%
Tetanus	%≥0.1IU/mL	5%	Diff=0%	100%	240/120	>99.9%
PT	GMC	1.5	Ratio=0.8	SD: 0.31535	480/240	88.7%
FHA	GMC	1.5	Ratio=0.84	SD: 0.3111	480/240	98.3%
PRN	GMC	1.5	Ratio=0.83 ^b	SD: 0.43427	480/240	79.1%
HepB	%≥10.0mIU/mL	10%	diff=-2%	97.7%	120/120	93.5%
Hib	%≥0.15µg/mL	5%	diff=0% ^a	96.6%	360/240	91.2%
	%≥1µg/mL	10%	diff=0%	81.2%	360/240	86.7%

Abbreviations: SD, standard deviation; GMC, geometric mean concentrations; PT, pertussis toxin; FHA, Filamentous hemagglutinin; PRN, pertactin; HepB, Hepatitis B; Hib, Haemophilus influenzae type B; diff, difference

Note: The sources are V72P13 clinical study report and the package insert of vaccines, unless otherwise indicated.

SDs for Pertussis were taken from GSK study Hib-97.

^aSource: V72P12 CSR.

^b Source: V72P16 Table 14.2.1.14 Group B+OMV versus MenC.

* Considering an estimated drop-out rate of 40%.

Table 22 Non-inferiority to Each Individual Antigen in MMR II and Varivax, at One Month After 4th Dose of rMenB+OMV NZ

Component	Endpoint	Non-inferiority Margin	Reference		# Evaluable Subjects per Immunogenicity Subset (MenB group/Placebo group)*	Power
			Ratio (co-ad vs routine)	SD		
Measles	GMC	1.5	ratio=0.9	SD: 0.45 ^a	480/240	95.5%
Mumps	GMC	1.5	ratio=0.9	SD: 0.38 ^a	480/240	99.1%
Rubella	GMC	1.5	ratio=0.9	SD: 0.34 ^a	480/240	99.8%
Varicella	GMC	1.5	ratio=0.9	SD: 0.45 ^b	480/240	95.5%

a Reference for sample size calculation: GSK Study MMR-161.

b Reference for sample size calculation: GSK Study MMR-160.

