9.5.2. Between groups assessment

For PCV antigens, at each blood sampling timepoint and for each antibody for which results are available, for Diphtheria, Tetanus, Pertussis and Hepatitis B antigens, at blood sampling timepoint one month after the 3rd vaccination, for VV and MMR, at blood sampling timepoint one month after the 4th vaccination and for each antibody for which results are available:

- The CIs of the between-group GMC ratios (i.e. study group minus control group) will be computed using an analysis of variance (ANOVA) model on the logarithm10 transformation of the concentrations.

For Diphtheria, Tetanus, Hib, Polio and Hepatitis B antigens, at blood sampling timepoint one month after the 3rd vaccination, for VV and MMR, at blood sampling timepoint one month after the 4th vaccination and for each antibody for which results are available:

- The CIs of the between-group percentage differences (i.e. study group minus control group) will be computed.

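### The non-inferiority model for the four MMR/VV GMC ratios leaves out the pre-dose concentration already measured at Visit 5: a cheap but probably small gain in precision goes unused

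*SAP*

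**What the plan says.** Protocol Section 2 makes the MMR/VV comparison a secondary non-inferiority objective, met if "the lower limit of the 2-sided 95% CI for the between-group ratio of GMCs is >0.67" one month after vaccination. Protocol 9.5.2 says the intervals for the GMC ratios "will be computed using an analysis of variance (ANOVA) model on the logarithm10 transformation of the concentrations". SAP 5.3.2 fills in the terms: the log10 values "will be analysed using an additive two-way Analysis of Variance (ANOVA) model which includes the vaccine-group effect, and a center effect". Neither document adds a pre-dose covariate.

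The pre-dose value exists. Protocol 5.2.3 states "Testing of MMR and VV will be done at Visit 5 (pre-4th vaccination) and Visit 6 (post-4th vaccination", and footnotes to Protocol Table 3 and SAP Table 3 put each draw before any vaccination at that visit. Its planned uses are by-timepoint summaries and within-group ratios (SAP 5.3.1.1), the same two-term ANOVA applied to the pre-4th-dose values, and picking out seronegative infants for the descriptive seroresponse endpoint (both SAP 5.3.2).

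Protocol Table 22 gives the planning figures, for example "Measles GMC 1.5 ratio=0.9 SD: 0.45 ^a 480/240 95.5" (per cent power) for measles. Protocol 9.1 applies no multiplicity adjustment to the secondary objectives.

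**The concern.** When the same antibody is measured before and after a single dose, the pre-dose value can explain part of the between-infant spread in the post-dose value. A model that omits it keeps that spread in the residual, so the interval for the GMC ratio is wider than it need be. At stake is the width of the interval judged against 0.67, which matters most for measles and varicella, the two antigens with the largest planning SD. The point is confined to MMR/VV: no blood is drawn before the first dose, so the post-dose-3 non-inferiority comparisons have no pre-vaccination value to adjust for.

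**Working it through.** **Inputs.** From Protocol Table 22: true ratio 0.9, margin 1.5 (taken as 1/1.5), 480/240 evaluable; log10 SD 0.45 (measles, varicella), 0.38 (mumps), 0.34 (rubella). From Protocol Section 2: two-sided 95% CI, that is, one-sided 0.025.

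**Step 1: reproduce the plan's power.** The distance to the margin is log10(0.9 × 1.5) = 0.1303. For SD 0.45, SE = 0.45 × √(1/480 + 1/240) = 0.0356, so the noncentrality is 0.1303/0.0356 = 3.66. With 718 df, power is 95.5%. The same steps give 99.1% for mumps and 99.8% for rubella. All four entries of Table 22 reproduce. With the margin read literally as 0.67, measles and varicella give 94.9%.

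**Step 2: add the pre-dose covariate.** Let r be the within-group correlation of log10 Visit 5 and log10 Visit 6 values. The residual SD becomes SD × √(1 − r²), with one degree of freedom fewer (717). Because r is not in the documents, a range is shown:

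| r (assumed) | Variance removed (r²) | Measles, varicella | Mumps | Rubella |
|---|---|---|---|---|
| 0 | 0% | 95.5% | 99.1% | 99.8% |
| 0.1 | 1% | 95.7% | 99.2% | 99.8% |
| 0.2 | 4% | 96.2% | 99.3% | 99.9% |
| 0.3 | 9% | 97.0% | 99.5% | 99.9% |
| 0.5 | 25% | 98.8% | 99.9% | >99.9% |

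These are noncentral-t values. The normal approximation gives 95.6% at r=0 and 95.8% at r=0.1, so the gain at r=0.1 is about 0.2 points either way.

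**Step 3: other ways to see the size.** For SD 0.45 the smallest observed ratio that passes is 10^(log10(1/1.5) + 1.96 × SE): 0.783 at r=0, 0.777 at r=0.3 and 0.766 at r=0.5. If all four antigens must pass, and they are treated as independent (an assumption), joint power is the product of the four: 0.955 × 0.955 × 0.991 × 0.998, about 90% at r=0. It becomes about 92% (r=0.2), 93.5% (r=0.3) and 97.5% (r=0.5).

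**Step 4: a less favourable true ratio.** At 0.85 (a scenario of mine; the plan uses 0.9), measles and varicella power goes from 84.2% to 87.4% (r=0.3) or 92.8% (r=0.5).

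**Step 5: values below the LLOQ.** Prior MMR or VV is an exclusion criterion (Protocol 4.3), so many pre-dose values may fall below the assay limits in SAP 5.3.2. A simulation of bivariate normal values, with values below the LLOQ set to half of it and 80% to 95% of infants below it (all assumptions), cuts a latent r of 0.3 to about 0.22–0.14 and a latent r of 0.5 to about 0.36–0.24. Through Step 2, measles and varicella power is then about 96.3%–95.9% and 97.5%–96.5% respectively.

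**The case against.** The strongest reply is that nothing is broken. A group-plus-center ANOVA is a valid randomized comparison, it is prespecified, and power is already 95.5% or more per antigen on the plan's own assumptions. The benefit rests on a correlation that appears nowhere in the documents, and in unvaccinated infants it may be close to zero. All of that stands, and it is why this is an optional improvement.

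Three further points also stand in part.

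- Visit 5 comes after randomization and after three doses of rMenB+OMV NZ or placebo, so it is not a strict baseline. It does precede MMR/VV, which makes adjustment defensible, but not free.
- In the subsets tested for MenB, MMR/VV rank below MenB for serum at Visit 5 (Protocol Table 9), with about 2 mL of serum per draw (Protocol 5.6.11.1). Some pre-dose values will probably be missing. A complete-case ANCOVA would lose those infants, while filling the gaps collides with Protocol 9.3, which rules out imputation.
- The pre-dose data are not idle. A group difference at Visit 5 would show in the planned pre-4th-dose analysis. It is only the non-inferiority model that does not use them.

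A reader might infer that the planned comparison is biased, or that residual maternal antibody guarantees a sizeable gain. The documents support neither. Randomization protects the unadjusted ratio, and neither document mentions maternal antibody or gives a pre/post correlation.

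**Conclusion.** The omission is real and the remedy is cheap, but the benefit is uncertain and probably modest. For measles and varicella the gain at the planned ratio runs from about 0.2 points (r=0.1) to 3.3 points (r=0.5). For mumps and rubella it is under 1 point throughout. If most infants are below the LLOQ before vaccination, the low end is the more likely. The figures rest on Table 22's SDs, ratio and evaluable numbers, and on an assumed r.

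It may be tempting to present the r=0.5 row as the expected gain, equivalent to 1/(1 − 0.25) = 1.33 times the subjects. Nothing in the documents supports choosing that row. Nor do they show that the MMR/VV objective is underpowered: its planned per-antigen power is 95.5% to 99.8%.

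**What to change.** Before unblinding, add to SAP 5.3.2, for measles, mumps, rubella and VZV only, an ANCOVA on log10 Visit 6 concentration with vaccine group, center and log10 Visit 5 concentration. Report the planned group-plus-center ANOVA alongside, and state in advance which of the two decides the 0.67 criterion.

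Two data rules are needed.

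- **Below the LLOQ:** use the SAP's below-cut-off value plus a below-LLOQ indicator. Protocol 9.3 leaves that value to the SAP, and I do not find it in the SAP text, where Annex 1 lists only references. It should be written down.
- **Missing Visit 5 value:** either define a missing-indicator rule and reconcile it with the no-imputation statement in Protocol 9.3, or leave those infants out of the ANCOVA and rely on the unadjusted ANOVA, which keeps them.

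The cost is one covariate and its indicator, with no new samples and no alpha. The downsides should be stated in the SAP: Visit 5 is a post-randomization measurement, although before MMR/VV, and the move away from the protocol's ANOVA must be recorded in SAP section 8.

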9. STATISTICAL METHODS

9.1. Determination of sample size

The study sample size was determined by the revised study design while maintaining an adequate study power to achieve all co-primary objectives previously discussed with CBER. The multiplicity issue was dealt with by controlling the global α at the level of 0.05 for all associated statistical hypotheses. This reduced number will also allow for enrolment of the minimum number of subjects exposed to rMenB+OMV NZ to fulfill initial Pediatric Study Plan (iPSP) commitment. The sample sizes were also calculated for the secondary objectives to evaluate the non-inferiority of RIV antigens. The evaluation will be performed by calculating the between-group differences/ratios and their 2-sided 95% CI. Therefore, no multiplicity was adjusted for the secondary objectives.

Study Sample Size Determination by Co-Primary Objectives

For the immune response to PCV13, sample size calculations were based on data from the PCV13 package insert and for the immune response to rMenB+OMV NZ sample size calculations were based on data from the previous GSK (legacy Novartis) V72P13 and V72P13E1, and from V72_56 study.

Using the procedure described in this section, the power for the study is presented in [Table 17](#). In case of 40% drop-out rate and 1200 subjects to be enrolled in a 2:1 ratio, it's assumed that 480 evaluable subjects from Group MenB+PCV and 240 evaluable subjects from Group Placebo+PCV could participate with data to the analyses. For PCV13 antigens a sample size of 240 will have approximately 99% power to show non-inferiority for all antigens. For MenB strains it's assumed that 480 evaluable samples from Group MenB+PCV will be evaluated in the analyses. With 240 per group for PCV13 antigen tests and 480 evaluable subjects from Group MenB+PCV for rMenB+OMV NZ strain tests, there is approximately 99% probability to reject all 23 null hypotheses, and to claim that the primary objectives of the study will be met according to the predefined success criteria.

Table 17 Power to Show Non-Inferiority PCV13 Co-Primary Objective and Sufficiency rMenB+OMV NZ Co-Primary Objectives

Co-Primary Objective	Power
Non-inferiority for GMCs for 13 antigens after the 3 rd vaccination	99.0%
Sufficiency for % of subjects with titers \geq LLOQ per each strain and all 4 strains combined (composite response) after the 3 rd vaccination	99.8%

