#### **5.3.1.1. Within groups assessment**

For each study group the following endpoints will be assessed related to MenB strains and PCV13 strains:

- the percentage of subjects with hSBA titers  $\geq$  LLOQ for each of the M14459, 96217, NZ98/254 and M13520 test strains and for all strains combined, at each timepoint that a blood sample result will be available
- the percentage of subjects with hSBA titers  $\geq 5$ ,  $\geq 8$  and  $\geq 16$  for each of the M14459, 96217, NZ98/254 and M13520 test strains, at each timepoint that a blood sample result will be available
- the percentages of subjects with hSBA titers  $\geq 8$  for each of the test strains (M14459, NZ98/254 and M13520),  $\geq 16$  for test strain 96217, and for all strains combined (composite endpoint) at one month after the 4th vaccination

- the percentage of subjects with 4-fold increase at post-4th (from pre-4th vaccination) for each of the M14459, 96217, NZ98/254 and M13520 test strains
- GMCs/GMTs and within group GMRs (for post-4th versus pre-4th titers) will be tabulated for antibodies for each antigen, at each timepoint that a blood sample result will be available
- Percentage of subjects with serum pneumococcal anti-capsular polysaccharide IgG  $\geq 0.35$   $\mu$ g/mL at one month after the 3rd and 4th vaccination in Group MenB+PCV and Group Placebo+PCV.

The CIs will be calculated as 2-sided 95% for exploratory objectives and will be calculated at given alpha at the testing step for the primary objectives that are associated with statistical hypothesis testing.

Endpoints associated with the other RIV will be assessed within-group as specified in Section 3. The 2-sided 95% CIs will be calculated.

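### The SAP's single ANOVA for hSBA titres gives MenB-vaccinated and MenB-unvaccinated infants one residual variance, so the 95% CIs for GMTs can miss their stated coverage by up to about 3 points

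*SAP*

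**What the plan says.** SAP 5.3.2 sets the model for log10 titres and concentrations after dose 3, before dose 4 and after dose 4: an "additive two-way Analysis of Variance (ANOVA) model which includes the vaccine-group effect, and a center effect". Its output is adjusted GMTs and GMCs, and "adjusted ratios of GMTs / GMCs for each vaccine group". A vaccine-group effect can be estimated only if both groups are in the fit. No unequal-variance option and no exception for hSBA is stated.

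The Statistical Methods part of SAP 5.3.1.4 says that the intervals for geometric means, and for the within-subject ratios after versus before dose 4, are "computed by exponentiating (base 10) the corresponding means and 95% CIs from an ANOVA model". SAP 5.3.1.1 sets the confidence level: "The CIs will be calculated as 2-sided 95% for exploratory objectives".

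Placebo hSBA data will exist. Protocol 5.2.3 says that subset B1 of the placebo group "will also be tested against the 4 serogroup B strains at all 3 timepoints", to keep the testing observer-blind. Protocol Table 8, footnote b, puts B1 at 200 infants, 120 of them evaluable. For the vaccinees, Protocol 9.1 plans on "480 evaluable subjects from Group MenB+PCV and 240 evaluable subjects from Group Placebo+PCV".

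**The concern.** A standard ANOVA estimates one residual variance and uses it for every group's interval. That is reasonable for antigens given to both arms, such as PCV13, pertussis or MMR. For hSBA the arms differ in kind: one has been immunised against the test strains and the other has not. Many unvaccinated infants can be expected to fall below the assay limit and share one substituted value, which would make their spread small. The pooled variance would then understate the vaccinees' variability and overstate that of the placebo infants.

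The hSBA GMTs at Days 151, 301 and 331, and the GMRs across dose 4, are listed secondary endpoints for the vaccine under study. They carry no success criterion, so the interval is the only inference reported for them and its stated 95% level should be right.

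**Working it through.** **Inputs**
- Evaluable numbers: Protocol 9.1 ("In case of 40% drop-out rate and 1200 subjects to be enrolled in a 2:1 ratio") and Protocol Table 8, footnote b.
- SD of log10 titre in vaccinees, Protocol Table 18. After dose 3: M14459 0.32193, 96217 0.36900, NZ98/254 0.51670, M13520 0.45023. After dose 4: 0.45097, 0.63454, 0.53796, 0.36477.
- SD of log10 titre in placebo infants: not in the documents. It is treated below as an assumption and varied. It also depends on the value substituted for titres below the cut-off. Protocol 9.3 leaves that value to the SAP, and the SAP's immunogenicity sections do not give one.

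**The plan's own figures.** 800 × 0.6 = 480 and 200 × 0.6 = 120, as stated. The documents set no precision target for hSBA GMTs. As a check on the planning means and SDs, the probability of rejecting all 23 hypotheses was recomputed as about 98.1–99.1%, against the stated 98.8%.

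**Formulas**, with nA = 480, nB = 120, vaccinee SD sA, placebo SD sB and r = sB/sA; centre terms are left out:
- k = pooled SD / sA = √[(479 + 119 r²)/598]
- width of the pooled CI relative to the group's own CI = k × t(598)/t(479) = k × 1.9639/1.9649
- coverage of the nominal 95% CI ≈ 2Φ(1.9639 k) − 1

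**Results for the MenB+PCV interval**

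| r | k | Coverage |
|---|---|---|
| 0 | 0.895 | 92.1% |
| 0.25 | 0.902 | 92.3% |
| 0.5 | 0.922 | 93.0% |
| 0.75 | 0.955 | 93.9% |
| 1 | 1.000 | 95.0% |
| 1.25 | 1.054 | 96.2% |

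At r = 0 the relative width is 0.895 × 0.9995 = 0.8945. The narrowing therefore cannot exceed about 10.5%, and undoing it widens the interval by 1/0.8945 − 1 ≈ 12%.

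**By strain, for assumed placebo SDs.** At 0.3, k after dose 3 is 0.987 for M14459 (coverage 94.7%) and 0.932 for NZ98/254 (93.3%). At 0.4, k for M14459 after dose 3 is 1.053 (96.1%), so that interval is too wide. The intervals for 96217 after dose 3 and M13520 after dose 4 also become slightly too wide, with k about 1.02 in both.

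**On the titre scale, worst case** (NZ98/254 after dose 3, sB = 0): GMT 14.40, with own-variance CI 12.94–16.02 and pooled CI 13.09–15.84.

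**Placebo interval.** With sA = 0.45 and sB = 0.10, the pooled SD is 0.405, so the placebo CI is about 4.0 times too wide. With sB = 0.20, the pooled SD is 0.413 and the factor is about 2.0.

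**Simulation check.** In 3,000 trials per scenario, titres below the LOD were set to LOD/2 (an assumption). With 0–5% of placebo infants above the LOD, coverage was about 91–93%. With 40% above it, the dose-3 intervals for M14459 and 96217 became slightly too wide (×1.05 and ×1.02).

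**The case against.** The strongest reply is that nothing decided in this trial depends on these intervals. That is correct. The ten confirmatory hSBA tests concern percentages, and SAP 5.3.1.4 gives binary endpoints Clopper-Pearson limits, which use no ANOVA variance. Protocol 9.7 treats analyses without a success criterion as descriptive. Even the worst case shifts a GMT limit only slightly. A reader might infer that the sufficiency conclusions are at risk; they are not.

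A second reply is that the direction is unproven. A reader might infer that the MenB+PCV intervals are certainly too narrow. The documents do not support that, because they give no placebo SD, and the error vanishes at equal SDs and reverses beyond that. The Table 18 SDs are also upper limits of two-sided 80% intervals. True vaccinee SDs may be smaller, which would raise r for any non-zero placebo SD and shrink the narrowing.

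A third reply is that the SAP may intend by-group fits. SAP 5.3.1.1 lists GMTs and within-group GMRs for each study group, and the between-group ANOVA list in SAP 5.3.1.2 does not name MenB. This carries weight for the GMRs, whose model is described only as an ANOVA. For GMTs it does not remove the problem: SAP 5.3.2 speaks of titres, includes the pre-dose-4 timepoint and asks for adjusted GMTs from a model with a group effect.

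The placebo hSBA intervals matter little in themselves, since B1 is tested only to protect blinding.

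**Conclusion.** The point holds in conditional form. As written, SAP 5.3.2 applies one residual variance to hSBA titres from about 480 vaccinated and 120 unvaccinated infants, and no other section provides for unequal variances. If the placebo SD is below the vaccinee SD, the MenB+PCV GMT intervals are too narrow by at most about 10.5%, with coverage from about 92% up to 95%, and the placebo intervals are too wide. If it is above, the direction reverses.

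These figures rest on the planned evaluable numbers, an assumed placebo SD and a calculation without centre effects. No claim is made about the centre term itself. For Day 301 the pooling follows from SAP 5.3.2, but Table 18 has no pre-dose-4 SD, so only the ratio-based bounds apply. For the GMRs, pooling across arms is an inference from the wording that ties them to the GMT method. The documents give no SD for the within-subject log ratio, so no size can be stated.

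This is a modest correction to descriptive secondary intervals. It is worth making because the remedy is valid whatever the placebo SD proves to be.

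**What to change.** Add one sentence to SAP 5.3.2 for hSBA, before unblinding. Either compute GMT and GMR CIs within each vaccine group (a t-interval on log10 values, or a centre-only model per group), or fit the group-plus-centre model with a separate residual variance per vaccine group. State explicitly that the choice covers the post/pre-dose-4 GMRs. Keep the pooled-variance ANOVA for antigens given to both arms (PCV13, diphtheria, tetanus, pertussis, hepatitis B, MMR, varicella).

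The cost is that sentence and one model option, with no new data. The MenB+PCV intervals become about 0–12% wider for placebo/vaccinee SD ratios from 1 down to 0, and slightly narrower if the placebo SD turns out larger.
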